ADA=anti-drug antibody; ASTCT=American Society for Transplantation and Cellular Therapy; CLND=completion lymph node dissection; CR=complete response; CRS=cytokine-release syndrome; EFS=event-free survival; NCI CTCAE v5.0=National Cancer Institute Common Terminology Criteria for Adverse Events, Version 5.0; ORR=objective response rate; OS=overall survival; pCR=pathologic complete response; PK=pharmacokinetic; pnCR=pathologic near complete response; pPR=pathologic partial response; PR=partial response; pRR=pathologic response rate; RECIST v1.1=Response Evaluation Criteria in Solid Tumors, Version 1.1; RFS=relapse-free survival.

Table 2 Objectives and Corresponding Endpoints for Cohort 1 (cont.)

Safety Objective	Corresponding Endpoints

• To evaluate the safety of treatment	
• Incidence, nature, and severity of adverse events and laboratory abnormalities, with severity determined according to NCI CTCAE v5.0 CRS severity will also be determined according to the ASTCT CRS Consensus Grading Scale.• Incidence and nature of immune-related adverse events Grade ≥ 3 during the first 12 weeks• Rate and duration of delayed surgery due to treatment-related adverse events• Surgical complication rates according to Clavien-Dindo surgical classification after CLND
Exploratory Pharmacokinetic Objectives	Corresponding Endpoints

• To characterize the PK profile of drugs that are administered as part of treatment	
• Plasma or serum concentration of each drug (as appropriate) at specified timepoints

• To evaluate potential relationships between drug exposure and the efficacy and safety of treatment	
• Relationship between plasma or serum concentration or PK parameters for each drug (as appropriate, on the basis of available data) and efficacy endpoints• Relationship between plasma or serum concentration or PK parameters for each drug (as appropriate, on the basis of available data) and safety endpoints
Exploratory Immunogenicity Objectives	Corresponding Endpoints

• To evaluate the immune response to drugs that are administered	
• For drugs for which ADA formation is measured: Presence of ADAs during the study relative to the presence of ADAs at baseline

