3.1.5 Assessments and Monitoring

All patients will be closely monitored for adverse events throughout the study. Adverse events will be graded according to the National Cancer Institute Common Terminology Criteria for Adverse Events, Version 5.0 (NCI CTCAE v5.0). CRS severity will also be graded according to the American Society for Transplantation and Cellular Therapy (ASTCT) CRS Consensus Grading Scale.

Patients in Cohort 1 will receive neoadjuvant treatment for 2 cycles (6 weeks) and will undergo surgery (CLND) in Week 7. All patients are expected to proceed with surgery, provided that there are no distant metastases and the surgeon considers the disease to be completely resectable. Pathologic response will be assessed locally and by independent pathologic review.

Patients who discontinue treatment due to unacceptable toxicity and continue to have no evidence of metastatic disease will still be eligible for surgery and proceed with CLND after the adverse event has resolved and re-staging confirms Stage III disease.

If patients have confirmed disease progression, patient management and treatment selection will be at the discretion of the treating physician. These patients will remain in the study for follow-up.

Patients will undergo radiological tumor assessments in Week 6 (from Day 1 of Cycle 1) prior to surgery (CLND) (see Section [4.5.7](#) for details). Response will be assessed and

determined by the investigator in accordance with RECIST v1.1, but confirmation by later imaging studies is not required (see [Appendix 1](#)).

Patients in Cohort 2 will undergo tumor assessments every 9 weeks (from Day 1 of Cycle 1) for the first 54 weeks and then every 12 weeks thereafter (see Section [4.5.7](#)). Response will be assessed by the investigator using RECIST v1.1 (see [Appendix 1](#)). Response per modified RECIST v1.1 for immune-based therapeutics (iRECIST) (see [Appendix 2](#)) will be determined programmatically by the Sponsor on the basis of investigator-assessed individual lesion data.

For Cohort 1 and Cohort 2, if clinical activity is demonstrated in an experimental arm, the Sponsor may request that tumor assessment scans for that arm and the corresponding control arm be submitted for evaluation by an independent review facility.

For all patients, blood samples will be collected at baseline and during the study for biomarker research, including blood-based next-generation sequencing (NGS) and circulating tumor DNA (ctDNA) testing.

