5.2.3 Adverse Events of Special Interest (Immediately Reportable to the Sponsor)

Adverse events of special interest are required to be reported by the investigator to the Sponsor immediately (i.e., no more than 24 hours after learning of the event; see Section 5.4.2 for reporting instructions). Adverse events of special interest for each treatment arm are listed in the respective appendix for that treatment arm (see [Appendix 11](#) through [Appendix 16](#)).

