5.3.1 Adverse Events Reporting Period

Investigators will seek information on adverse events at each patient contact. All adverse events, whether reported by the patient or noted by study personnel, will be recorded in the patient's medical record and on the Adverse Event eCRF.

After informed consent has been obtained but prior to initiation of study treatment, only serious adverse events caused by a protocol-mandated intervention (e.g., invasive procedures such as biopsies, discontinuation of medications) should be reported (see Section 5.4.2 for instructions for reporting serious adverse events).

After initiation of study treatment, all adverse events will be reported until 30 days after the final dose of study treatment or until initiation of new systemic anti-cancer therapy, whichever occurs first, and serious adverse events and adverse events of special interest will continue to be reported until 135 days after the final dose of study treatment or until initiation of new systemic anti-cancer therapy, whichever occurs first.

Instructions for reporting adverse events that occur after the adverse event reporting period are provided in Section 5.6.

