5.6 ADVERSE EVENTS THAT OCCUR AFTER THE ADVERSE EVENT REPORTING PERIOD

After the end of the reporting period for serious adverse events and adverse events of special interest (defined as 135 days after the final dose of study treatment or until initiation of new, systemic anti-cancer therapy, whichever occurs first), all deaths, regardless of cause, should be reported through use of the Long-Term Survival Follow-Up eCRF.

After the end of the reporting period for non-serious adverse events (defined as 30 days after the final dose of study treatment), all treatment-related non-serious adverse events that lead to surgery delay will continue to be reported until 135 days after the final dose of study treatment.

In addition, if the investigator becomes aware of a serious adverse event that is believed to be related to prior exposure to study treatment, the event should be reported through use of the Adverse Event eCRF. However, if the EDC system is not available, the investigator should report these events directly to the Sponsor or its designee, either by

faxing or by scanning and emailing the paper Clinical Trial Adverse Event/Special Situations Form using the fax number or email address provided to investigators.

5.7 EXPEDITED REPORTING TO HEALTH AUTHORITIES, INVESTIGATORS, INSTITUTIONAL REVIEW BOARDS, AND ETHICS COMMITTEES

The Sponsor will promptly evaluate all serious adverse events and adverse events of special interest against cumulative product experience to identify and expeditiously communicate possible new safety findings to investigators, IRBs, ECs, and applicable health authorities based on applicable legislation.

To determine reporting requirements for single adverse event cases, the Sponsor will assess the expectedness of these events through use of the reference safety information in the documents listed below:

- Opdivo® EMA Summary of Product Characteristics (SmPC; nivolumab)
- Yervoy® EMA SmPC (ipilimumab)
- RO7247669 Investigator's Brochure
- Atezolizumab Investigator's Brochure
- Tiragolumab Investigator's Brochure

The Sponsor will compare the severity of each event and the cumulative event frequency reported for the study with the severity and frequency reported in the applicable reference document.

Reporting requirements will also be based on the investigator's assessment of causality and seriousness, with allowance for upgrading by the Sponsor as needed.

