6.5 SAFETY ANALYSES

Verbatim adverse event terms will be mapped to Medical Dictionary for Regulatory Activities thesaurus terms, and adverse event severity will be graded according to NCI CTCAE v5.0 and also according to the ASTCT CRS Consensus Grading Scale for CRS.

Safety will be assessed through summaries of adverse events, changes in laboratory test results, changes in vital signs and ECGs, and exposure to study drugs. Exposure to combination treatment and length of safety follow-up will be summarized by treatment arm.

All verbatim adverse event terms will be mapped to Medical Dictionary for Regulatory Activities thesaurus terms. Adverse event severity will be graded according to NCI CTCAE v5.0, and severity of CRS will also be graded by the investigator according to the ASTCT Consensus Grading (Lee et al. 2019). All adverse events, serious adverse events, adverse events leading to death, adverse events of special interest, and adverse events leading to study treatment discontinuation that occur on or after the first dose of study treatment (i.e., treatment-emergent adverse events) will be summarized by mapped term, appropriate thesaurus level, and severity grade. For events of varying severity, the highest grade will be used in the summaries. Deaths and causes of death will be summarized.

Relevant laboratory, vital sign (pulse rate, respiratory rate, blood pressure, pulse oximetry, and temperature), and ECG data will be displayed by time, with grades identified where appropriate. Additionally, a shift table of selected laboratory test results will be used to summarize the baseline and maximum postbaseline severity grade. Changes in vital signs and ECGs will be summarized.

Additionally, in Cohort 1, the incidence, nature of immune-related adverse events Grade ≥ 3 during the first 12 weeks, and the rate and duration of delayed surgery due to treatment-related adverse events will be summarized by treatment arm. CLND may be delayed for up to 2 weeks if study treatment-related adverse events have not improved sufficiently at the time of planned surgery (see Section 3.1.3).

Additionally, surgical complications will be scored according to Clavien-Dindo classification ([Appendix 5](#)). Complication rates for every grade will be reported and scored for patients that underwent CLND.

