Appendix 11: Study Details Specific to Nivo+Ipi Arm (Control)

A11–5 ASSESSMENT OF SAFETY FOR NIVO+IPI ARM

A11–5.1 SAFETY PLAN FOR NIVO+IPI ARM

Measures will be taken to ensure the safety of patients participating in this study, including the use of stringent inclusion and exclusion criteria and close monitoring of patients during the study. Administration of study treatment will be performed in a monitored setting in which there is immediate access to trained personnel and adequate equipment and medicine to manage potentially serious reactions. Adverse events will be reported as described in Sections 5.2–5.6.

For detailed safety information, refer to the local prescribing information for each agent.

A11–5.1.1 Risks Associated with Nivolumab

Nivolumab has been associated with risks such as infusion-related reactions (IRRs) and immune-mediated adverse events. Refer to the local prescribing information for nivolumab for a detailed description of anticipated safety risks for nivolumab.

A11–5.1.2 Risks Associated with Ipilimumab

Ipilimumab has been associated with risks such as IRRs and immune-mediated adverse events. Refer to the local prescribing information for ipilimumab for a detailed description of anticipated safety risks for ipilimumab.

A11–5.1.2.1 Risks Associated with Combination Use of Nivolumab and Ipilimumab

Immune-related adverse reactions have occurred at higher frequencies in combination treatment of nivolumab with ipilimumab compared with either drug as monotherapy.

A11–5.1.2.2 Management of Patients Who Experience Adverse Events in Nivo+Ipi Arm

Guidelines for the management of patients who experience adverse events are provided in the local prescribing information for each drug.

A11–5.2 REPORTING REQUIREMENTS FOR PREGNANCIES IN NIVO+IPI ARM

A11–5.2.1 Pregnancies in Female Patients

Female patients of childbearing potential will be instructed through the Informed Consent Form to immediately inform the investigator if they become pregnant during the study or within 5 months after the final dose of nivolumab or within 5 months after the final dose of ipilimumab. A paper Clinical Trial Pregnancy Reporting Form should be completed and submitted to the Sponsor or its designee immediately (i.e., no more than 24 hours after learning of the pregnancy), either by faxing or by scanning and emailing the form using the fax number or email address provided to investigators. Pregnancy should not

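### The Cohort 1 endpoint of Grade ≥ 3 immune-related adverse events in the first 12 weeks outlasts the reporting of non-serious events, so it is incompletely ascertained

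*Combined protocol and SAP*

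**What the plan says.** Section 2 (Table 2) lists among the Cohort 1 safety endpoints "Incidence and nature of immune-related adverse events Grade ≥ 3 during the first 12 weeks". Section 6.5 repeats it without a collection rule of its own: these events "during the first 12 weeks, and the rate and duration of delayed surgery due to treatment-related adverse events will be summarized by treatment arm".

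Collection is governed elsewhere. Under Section 5.3.1, after treatment starts, "all adverse events will be reported until 30 days after the final dose of study treatment". Serious adverse events and adverse events of special interest (AESIs) continue to 135 days after the final dose. Both windows close early if new systemic anti-cancer therapy starts. Section 5.6 confirms the 30-day limit for non-serious events and makes one exception: "all treatment-related non-serious adverse events that lead to surgery delay will continue to be reported until 135 days after the final dose".

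On dosing, Section 3.1.5 states: "Patients in Cohort 1 will receive neoadjuvant treatment for 2 cycles (6 weeks) and will undergo surgery (CLND) in Week 7". Cycles are 21 days.

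On AESIs, Section 5.2.3 states: "Adverse events of special interest for each treatment arm are listed in the respective appendix for that treatment arm", and names Appendices 11 to 16. The safety part of the Appendix 11 contents list (A11-5) has a safety plan and pregnancy reporting, with no AESI entry. The text of A11-5.1 ends with "Guidelines for the management of patients who experience adverse events are provided in the local prescribing information for each drug" and moves straight to pregnancy reporting.

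**The concern.** The endpoint window and the reporting window have different anchors. The endpoint runs for a fixed 12 weeks; reporting of non-serious events runs for 30 days from whichever dose turns out to be the last. With two doses three weeks apart, the second closes well before the first.

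Serious-event reporting does not fill the interval, because Section 5.2.2 requires severity and seriousness to be judged separately, so a Grade 3 event need not be serious. For example, the Appendix 9 guidance on Grade 3 dermatologic events relies on specialist referral and corticosteroids and does not call for admission.

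The sponsor met the same problem with delayed surgery, the next endpoint in the same list, and closed it through Section 5.6. The 12-week endpoint was left as it was. At stake is a named measure of tolerability, and a natural one on which to set the experimental arms beside Nivo + Ipi. Events that were never collected are hard to recover at analysis.

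**Working it through.** The plan gives no figure of its own for this gap, so the check is calendar arithmetic.

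Inputs:
- Two 21-day cycles (Section 3.1.5; A11-4.1.2 for the control arm).
- Non-serious reporting to final dose + 30 days; serious events and AESIs to final dose + 135 days (Section 5.3.1).
- Endpoint window of 12 × 7 = 84 days, counted from Cycle 1 Day 1 (assumption).

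Check of the day count: 2 × 21 = 42 days puts surgery at Day 43 (Week 7). The completion visit 6 weeks later falls on 43 + 42 = Day 85 (Week 13). Both agree with the protocol's timetable.

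Formulas: planned final dose = 1 + 21 = Day 22; cut-off = final dose + 30; gap = 84 − cut-off.

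| Case | Final dose | Non-serious reporting ends | Gap to Day 84 | Share of calendar days | Serious/AESI reporting ends |
|---|---|---|---|---|---|
| Two doses on time | Day 22 | Day 52 | 32 days | 32/84 = 38% | Day 157 |
| Cycle 2 delayed 14 days (assumption) | Day 36 | Day 66 | 18 days | 18/84 = 21% | Day 171 |
| Cycle 2 omitted | Day 1 | Day 31 | 53 days | 53/84 = 63% | Day 136 |

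If the 12 weeks instead start at randomization, 7 days before the first dose (assumption), the window ends on Day 77 and the gap after two on-time doses is 77 − 52 = 25 days.

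What is still captured inside the gap, provided new systemic therapy has not started:
- serious events, including any that lead to hospitalization (Sections 5.2.2 and 5.3.5.11);
- Grade 4 and 5 events, which a footnote to Table 8 makes reportable as serious (the table is for events not listed in CTCAE, but the footnote is worded generally);
- Hy's Law cases, reported as serious or as AESIs in every arm (Section 5.3.5.7);
- AESIs, where an arm has a list;
- treatment-related non-serious events that delay surgery (Section 5.6);
- worsening of an event already open, whose peak grade is recorded (Section 5.3.5.4).

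What is lost is a new-onset, non-serious Grade 3 immune-related event that is not an AESI, does not meet Hy's Law and delays no surgery.

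Visits do not close the gap for everyone. Operated patients return in Week 13. Patients not operated on have their final treatment visit within 30 days of the last dose (Section 4.6.1), so no later than the reporting cut-off.

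**The case against.** The strongest reply is that the loss is narrow. All events are reported to Day 52 after two on-time doses, and the more serious later ones still come in by the routes listed above. This stands. A reader might infer from the mismatch that the endpoint cannot be ascertained at all; the documents do not support that.

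The percentages are also open to misreading. They are shares of calendar days, and several kinds of event are still reported on those days. Reading 38% or 63% as a share of events lost would be wrong. The documents give neither the timing of immune-related events nor the fraction that are non-serious.

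One might infer that patients stopped after one dose for toxicity are under-counted most. Their calendar gap is the longest, but if the toxicity that stopped treatment was itself a Grade ≥ 3 immune-related event, it fell inside the reporting window or was followed as an open event, and the patient already counts towards incidence. Greater under-counting in this group is possible but not shown.

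One might also infer that the control arm loses more events and so looks safer, since its appendix shows no AESI list. That depends on the AESI lists in Appendices 12 to 16 and on the footnotes to the Appendix 11 schedule of activities, none of which is in the text available for this review. A difference between arms cannot be verified in either direction.

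Finally, the endpoint is descriptive, the study has no hypothesis test (Section 6.1), and the enrollment hold rule in Section 3.1.3 has its own criteria. That limits the consequence but does not reconcile the two windows.

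**Conclusion.** The point holds as incomplete ascertainment. Followed as written, the plan does not collect new-onset, non-serious Grade 3 immune-related events from the non-serious cut-off to Day 84 unless they are AESIs, meet Hy's Law or delay surgery. The interval is 32 calendar days after two on-time doses, 53 if Cycle 2 is omitted, and 18 if Cycle 2 slips by 14 days. These figures assume that the 12 weeks start at Cycle 1 Day 1, which the protocol should state. The direction for the endpoint as a whole is under-counting; its size in events cannot be derived.

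Separately, Section 5.2.3 and Appendix 11 do not agree: the first promises a control-arm AESI list, and the contents list and visible safety text of the second have none. This is a cross-reference to be resolved, and the available text does not make it evidence of bias between arms.

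**What to change.** - In Sections 5.3.1 and 5.6, extend the existing surgery-delay exception so that all Grade ≥ 3 immune-related adverse events, serious or not, are reported in every Cohort 1 arm through at least Week 12, whatever the date of the last dose. This needs final dose + 62 days after two on-time doses (84 − 22) and + 83 after one (84 − 1); the 135-day window already in Section 5.6 covers both.
- State when the 12 weeks begin, and how the cut-off at new systemic anti-cancer therapy applies to this endpoint.
- Use one common list of immune-related terms for all arms, and reconcile Section 5.2.3 with Appendix 11.

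The alternative is to restate the window in Sections 2 and 6.5 as 30 days after the final dose. That matches collection, but observation time then varies with doses received (to Day 31 after one dose, Day 52 after two on time).

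The cost of the first option is protocol wording, eCRF guidance and slightly more adverse event entry. Operated patients can be covered at the existing Week 13 visit; patients not operated on need one adverse event contact at Week 12.
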